### **Protocol Maintenance**

Protocol modifications will be approved by the principal investigators and submitted to the Mayo Clinic IRB in accordance with Mayo IRB rules and regulations. Modifications will be documented separately and within the main protocol document with a newly assigned date and version number.

### **Study Registration**

The study will be submitted to clinicaltrials.gov.

## **Appendix – Case Report Forms**

### **Contact Information**

Name: \_\_\_\_\_  
(First) \_\_\_\_\_ (Last) \_\_\_\_\_

Home: (\_\_\_\_) \_\_\_\_\_ - \_\_\_\_\_ Work: (\_\_\_\_) \_\_\_\_\_ - \_\_\_\_\_

Mobile: (\_\_\_\_) \_\_\_\_\_ - \_\_\_\_\_ Email: \_\_\_\_\_

Address:  
\_\_\_\_\_ Unit/Apt# \_\_\_\_\_  
(Street)

City \_\_\_\_\_ State \_\_\_\_\_ Zip \_\_\_\_\_

## **Eligibility Criteria**

### **Inclusion Criteria (all must be “yes”)**

○ 18-65 years of age	Yes	No
○ Episodic or Chronic Migraine	Yes	No
○ 6-25 migraine days per month	Yes	No
○ Migraine started at least 12 months ago	Yes	No

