
[figure not shown]
**Figure 1:** Regions that allow for accurate discrimination of the chronic migraine brain from that of a healthy control. (20) Structural measures (i.e. cortical thickness, volume, surface area) of the colored brain regions allow for classification of the individual brain MRI as belonging to a person with chronic migraine vs. a healthy control with 86.3% average accuracy. Similar model-building techniques can be used to construct classifiers that predict response to erenumab.

[figure not shown]
**Figure 2:** Regions that allow for accurate discrimination of the chronic migraine brain from that of an episodic migraineur. (20) Structural measures (i.e. cortical thickness, volume, surface area) of the colored brain regions allow for classification of the individual brain MRI as belonging to a person with chronic migraine vs. episodic migraine with 84.2% average accuracy. Similar model-building techniques can be used to construct classifiers that predict response to erenumab.

**Figure 3:** Functional connectivity patterns for the left and right amygdala that contribute to the classification accuracy of distinguishing between individual migraine patients and individual healthy controls. (21) Whole-brain functional connectivity patterns of 6 regions distinguished migraine patients from healthy controls with a best classification accuracy of 86.1%. Migraineurs with longer disease durations were more accurately classified than migraine patients with shorter disease durations. Similar model building techniques could be used to track and predict response to erenumab treatment.

**Figure 4:** Key brain areas (based on brain structural imaging) and functional connections (based on resting-state imaging) that contribute to distinguishing migraine patients from healthy controls. (22) The combined model that included structural and functional data provided greater accuracy (83%) compared to the model based on structural data alone (80%) and the model built on functional connectivity data alone (75%). The combination of structural and functional brain imaging data may increase the classification accuracy for predicting/determining treatment response to erenumab.

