**Table 1- Study Flow.**

	Run in Phase (time: -4 wks)	Baseline (time: 0)	First Follow-up (time: 2 wks)	Second Follow-up (time: 4 wks)	Third Follow-up (time: 8 wks)	Fourth Follow-up (time: 12 wks)
Determine Eligibility	X	X				
Questionnaires	X	X	X	X	X	X
QST		X	X		X	
MR Imaging		X	X		X	
Cognitive Testing		X	X		X	
Vital Signs		X	X	X	X	X
Urine Pregnancy Test		X		X		
Erenumab Treatment		X		X		
Headache Diary	X	X	X	X	X	X

**Participants:** Up to 67 adult patients who are at least 18 years of age but younger than 66 years of age with high frequency episodic migraine or chronic migraine with and/or without aura will be enrolled into the run-in phase of this study at Mayo Clinic Arizona. Enrollment will stop once 50 subjects provide headache diary during the run-in phase that meets eligibility criteria (i.e. documented 6-25 migraine days per 28 days). Previously collected data of healthy control subjects (n=50) will be used for data comparison. Exclusion and inclusion criteria will be modeled after those used in the phase 2 and 3 trials of erenumab for the prevention of migraine. (6, 8) In addition, patients who have contraindications to MRI (e.g. metal implants, aneurysm clips, severe claustrophobia) will be excluded from study participation. Potential participants will be excluded if they have active chronic pain conditions other than migraine (e.g. chronic pelvic pain) or acute pain conditions (e.g. recent surgery). Potential participants who have sensory disorders that might affect the perception of cutaneous thermal stimuli will also be excluded (e.g. peripheral neuropathy).

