## **Subject Eligibility**

### *Inclusion Criteria*

- Adults 18-65 years of age

- Episodic migraine (with or without aura) or chronic migraine according to the diagnostic criteria included within the International Classification of Headache Disorders 3 (ICHD-3) (23)
  - Episodic Migraine
    - A. At least 5 attacks fulfilling criteria B-D
    - B. Headache attacks lasting 4-72 hours (when untreated or unsuccessfully treated)
    - C. Headache has at least two of the following four characteristics:
      - a. Unilateral location
      - b. Pulsating quality
      - c. Moderate or severe pain intensity
      - d. Aggravation or causing avoidance of routine physical activity
    - D. During headache at least one of the following:
      - a. Nausea and/or vomiting
      - b. Photophobia and phonophobia
    - E. Not better accounted for by another ICHD-3 diagnosis
  - Chronic Migraine
    - A. Headache (migraine-like or tension-type like) on at least 15 days per month for longer than 3 months, and fulfilling criteria B and C
    - B. Occurring in a patient who has had at least five attacks fulfilling criteria B-D for "episodic migraine" (above)
    - C. On at least 8 days per month for longer than 3 months, fulfilling any of the following:
      - a. Criteria C and D for migraine without aura
      - b. Criteria B and C for migraine with aura
      - c. Believed by the patient to be a migraine at onset and relieved by a triptan or ergot derivative
    - D. Not better accounted for by another ICHD-3 diagnosis
- 6-25 migraine days per month on average over the 3 months prior to screening, confirmed by run-in phase prospective data collection
- Duration since migraine onset of at least 12 months prior to screening based on medical records and/or patient self-report

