### Imaging Protocol

Brain MRI will be performed on a Siemens 3T scanner at the Mayo Clinic. The MRI paradigm will include: 1) high-resolution T1-weighted imaging allowing for advanced structural analyses such as determining regional volumes, cortical thickness and surface area; 2) T2-weighted imaging to rule out pre-existing structural brain abnormalities (e.g. incidental findings); 3) Diffusion Tensor Imaging (DTI) used for assessing white matter integrity; 4) ten minutes of resting-state Blood Oxygen Level Dependent (BOLD) signal collection for resting state functional connectivity analyses; 5) event-related paradigm during which patients are exposed to cutaneous thermal stimuli causing moderately intense heat pain so that brain responses to pain can be measured; and 6) Arterial Spin Labeling (ASL) to assess cerebral blood flow.

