#### Analysis Plans

*Specific Aim #1 (i.e. identify changes in brain structure and function that correlate with response to erenumab):* Pre-treatment and post-treatment MRI data will be used for within and between subject

comparisons. Within subject analyses will compare baseline brain activation and perfusion patterns and functional connectivity patterns pre-treatment to post-treatment. Between subject group analyses will compare post-treatment MRI data in erenumab responders to non-responders.

Similar comparisons will be made for pre- and post-treatment pain thresholds (i.e. results of quantitative sensory testing) and cognitive testing.

So as to help with the interpretation of differences between responders and non-responders, MRI data from erenumab-treated patients will be compared to healthy non-migraine control data that we have already collected during the conduction of previous studies, when available (although we have plenty of data for the majority of analyses, we have limited ASL data and no n-back data from healthy controls). Differences in brain structure and function of migraine patients prior to erenumab treatment compared to healthy controls will be identified. Results of this analysis will determine alterations of brain structure and functions in migraine patients compared to healthy controls. Areas where migraine patients show altered structure and function will be used as regions of interest (ROIs) to assess the longitudinal, within-group changes of erenumab responders and non-responders.

Although multiple analyses are planned using functional, structural, and perfusion data, the primary analysis for specific aim #1 will be the comparison of pre-treatment pain-induced regional activation strength vs. post-treatment pain-induced regional activation strength in erenumab responders and separately in erenumab non-responders.

Post-treatment changes in other measures of brain function as well as measures of brain perfusion, brain structure, cutaneous pain thresholds and cognitive function in those responding to erenumab and in those not responding will be explored.

Two-tailed T-Tests or Mann-Whitney U tests will be used to perform group comparisons on demographic and cognitive measures and on pain threshold data. Neuroimaging data will be analyzed using general linear model designs. Within-group changes on cognitive measures, sensory testing and neuroimaging data will be assessed by applying a general linear mixed model design.

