### **Headache Characteristics (structured interview)**

How many days per month (28 days) with headache of any kind/severity: \_\_\_\_\_ / 28 days

How many days per month (28 days) with complete headache freedom: \_\_\_\_\_ / 28 days

How long do headaches last if untreated/inadequately treated: hours

How long do headaches last if successfully treated: hours

Where are they usually located (circle all that apply):

Right                    Left                    Front                    Back                    Side

Unilateral location:                    Yes                    No

Quality (circle all that apply):

Pulsating/Throbbing                    Pressure/Aching                    Stabbing                    Burning

Intensity:  
Mild                    Moderate                    Severe

Average on 0 (no pain) to 10 (most severe pain) scale: /10

Maximum on 0 (no pain) to 10 (most severe pain) scale: /10

Headaches worse with physical activity:                    Yes                    No

Headache worse with mental activity:	Yes	No
Nausea:	Yes	No
Vomiting:	Yes	No
Sensitivity to light:	Yes	No
Sensitivity to sound:	Yes	No
Conjunctival injection:	Yes	No
Tearing:	Yes	No
Nasal congestion/rhinorrhea:	Yes	No
Eyelid drooping:	Yes	No
Auras with headaches:	Yes	No
Visual:	Yes	No
Sensory:	Yes	No
Motor:	Yes	No
Dysphasia:	Yes	No
Other:	Yes	No

Percentage of headaches you experience auras: \_\_\_\_\_

When was your first headache (month and year): \_\_\_\_\_

Family history of migraine: Yes No  
 If yes, who:

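### The responder v non-responder MRI comparison and the Aim 2 models pool episodic and chronic migraine with no term for subtype or baseline frequency, so part of a response signature could reflect subtype

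*Combined protocol and SAP*

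**What the plan says.** The Participants paragraph under Methods enrols patients with "high frequency episodic migraine or chronic migraine with and/or without aura". The Inclusion Criteria define the two diagnoses separately; the chronic one starts with "Headache (migraine-like or tension-type like) on at least 15 days per month for longer than 3 months" and also requires at least 8 migraine-type days per month over the same period. The eligibility form in the Appendix has a single yes/no item, "Episodic or Chronic Migraine", and no other case report form has a subtype field.

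Analysis Plans, Specific Aim #1, states: "Between subject group analyses will compare post-treatment MRI data in erenumab responders to non-responders". The same section makes a different comparison primary: pain-induced activation before v after treatment, within responders and separately within non-responders. Other measures are to be explored.

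Specific Aim #2 selects principal components that maximise cross-validated accuracy for response. The first tier is limited to T1 structural components, and later tiers add resting-state and more advanced imaging. Patient characteristics are mentioned only as something that may be included. Neither Sample Size nor Analysis Plans names subtype or baseline frequency as a covariate, stratum, subgroup or sensitivity analysis.

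Under Published Work and Preliminary Data, Figure 2 reports "classification of the individual brain MRI as belonging to a person with chronic migraine vs. episodic migraine with 84.2% average accuracy" from cortical thickness, volume and surface area. The Imaging Protocol obtains the same class of measures: "high-resolution T1-weighted imaging allowing for advanced structural analyses such as determining regional volumes, cortical thickness and surface area". The same background section says that, in several regions, the excess pain-induced activation in migraine correlated with headache frequency.

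**The concern.** A variable can pass for an imaging marker of response if it is visible on MRI and also related to response. The protocol's own background supplies the first half for subtype (structure) and for headache frequency (activation).

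The second half is not documented but cannot be ruled out. Daily Headache Diary defines response as a reduction of at least 50% from run-in migraine days, and run-in days may range from 6 to 25. A responder therefore needs 3 fewer days at one end of the range and 12.5 fewer at the other, so baseline frequency is built into the outcome.

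Two analyses are exposed:

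- The between-group comparison uses post-treatment scans rather than change, so stable differences between subtypes do not cancel.
- The Aim 2 algorithm would tend to keep a component that carries subtype whenever subtype relates to response. Cross-validation would not remove it, because the association is also present in the held-out patients.

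The imaging tiers are compared only with one another. The plan as written therefore cannot show that MRI adds to a diagnosis and a day count that need no scan, although Specific Aim #2 sets out to judge usefulness in clinical practice.

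**Working it through.** **1. The plan's own figures.** Sample Size gives 50 patients, 15% incomplete, about 50% responders, a 0.1% difference, SD 0.1, alpha 0.05, 21 per group and 88% power. Evaluable patients: 50 × 0.85 = 42.5, hence 21 and 21. A two-sided two-sample t-test with 21 per group and d = 0.1/0.1 = 1.0 gives 88.5%, so the stated power reproduces. The 84.2% is a result quoted from earlier work and cannot be recomputed.

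**2. How well subtype alone would predict response.** Assumptions not in the documents: a 50:50 mix, and response rates p and 1 − p in the two subtypes, which keeps the overall rate at the plan's 50%. A score that identifies subtype with accuracy 0.842 and knows nothing else classifies response with accuracy 0.842p + 0.158(1 − p).

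| Response rates | Accuracy of the imaging subtype score | Accuracy from the true diagnosis |
|---|---|---|
| 50/50 | 50.0% | 50% |
| 55/45 | 53.4% | 55% |
| 60/40 | 0.5052 + 0.0632 = 56.8% | 60% |
| 65/35 | 0.5473 + 0.0553 = 60.3% | 65% |
| 70/30 | 0.5894 + 0.0474 = 63.7% | 70% |
| 75/25 | 0.6315 + 0.0395 = 67.1% | 75% |

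With a 30:70 or 70:30 mix, gaps of 20, 40 and 50 points give 55.7%, 61.5% and 64.4%. In every row with a gap, knowing the diagnosis without a scan does better than the imaging score.

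**3. Chance imbalance.** Suppose subtype and response are unrelated and 42 patients split 21:21 on each. The subtype share then differs by at least 20 points between response groups in about 22% of samples, and by at least 30 points in about 6%. An unadjusted comparison can be tilted in a single study even without a true association.

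**4. What adjustment costs.** With a subtype covariate correlated r with response, the noncentrality is 1/√[(2/21)/(1 − r²)] on 39 degrees of freedom. Power is 88.5% at r = 0, 85.4% at r = 0.3 and 78.1% at r = 0.5. With both margins 50:50, r equals the gap in response rates, so 0.3 corresponds to 65/35 and 0.5 to 75/25. Any gain from reduced residual variance is ignored.

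**5. Can subtype be recovered?**

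- MIDAS, given at the first treatment visit, asks for headache days over the last 3 months.
- The structured interview asks "How many days per month (28 days) with headache of any kind/severity" at the first visit and again at the first treatment visit.
- The run-in diary records features, severity, duration and medication by day for 28 days.

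Together these approximate the chronic threshold. They do not strictly confirm it: MIDAS gives one total in a window that overlaps the run-in, and nothing records 8 migraine-type days per month for longer than 3 months.

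**The case against.** Most of the case on the other side narrows the point rather than removing it.

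- **Lost data.** A reader might infer from the merged item that subtype is irrecoverable. It is not; the three sources above allow a working classification. The gap is in the analysis plan and in the lack of an explicit field.
- **A decision already made.** A reader might suppose that the investigator must choose a subtype to complete the form. The episodic criteria set no upper limit on days, and chronic patients must have had attacks meeting the episodic features, so the item can be answered yes without choosing.
- **The primary analysis.** It is within-subject, so a stable difference between subtypes cancels. Only a change that itself depends on subtype would disturb it. This stands.
- **Prediction is not causal inference.** A model that works partly through subtype still predicts. This stands too, and it makes added value over clinical data the right question. The optional sentence on patient characteristics does not commit the plan to asking it.
- **Size.** It is tempting to say that the response signature could simply be a subtype signature, or to convert 84.2% into a separation of 2.0 SD. A t-test on such a score at 21 v 21 would then reach p<0.05 in about 15%, 28% or 46% of trials at 60/40, 65/35 or 70/30. But that score is optimised for subtype and no such test is planned. Single regions would be affected less. The 84.2% comes from an earlier sample, and separation may differ in high-frequency episodic patients. At n = 42 the standard error of an accuracy near 50% is √(0.25/42) = 7.7 points, so 57% is within one standard error of chance.

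**Conclusion.** The point holds for the non-primary responder v non-responder comparison and for Aim 2. Both pool the two diagnoses without a prespecified term for subtype or baseline frequency, while the protocol's own background says structure distinguishes the subtypes and activation tracks headache frequency.

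Under an assumed 50:50 mix and response rates of 60/40 to 70/30, subtype alone would give about 57% to 64% accuracy; with no gap it would give 50%. That is enough to account for a weak classifier. It is not enough for one at the 75% to 86% shown in Figures 1 to 4: even an assumed 50-point gap gives only 64% to 67%. The documents therefore support saying that part of a response signature could be subtype, but not that it would be nothing else.

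The result rests on response differing by subtype, on the assumed mix, and on the 84.2% carrying over to this sample; none of these can be checked in the documents. The primary Aim 1 analysis is largely unaffected. The change is worth making because it mostly uses data already collected.

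**What to change.** 1. Record episodic or chronic as its own field at screening, or state a rule deriving it from MIDAS, the structured interview and the run-in diary. Report it by response group.
2. In Analysis Plans, Specific Aim #1, add subtype or run-in migraine-day frequency as a covariate in the between-group general linear model, and name which one in advance.
3. In Specific Aim #2, place a clinical-only model (subtype and baseline frequency) ahead of the T1 tier as the first comparator. Report how well the chosen imaging score predicts subtype.
4. Report accuracy within each subtype as descriptive only. With about 21 patients per subtype the 95% interval is roughly ±1.96 × √(0.25/21) = ±21 points, too wide to settle whether MRI adds anything.

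The cost is one field, one degree of freedom, and one extra model and table. If subtype and response are correlated, power for the between-group comparison falls from 88.5% to 85.4% at a correlation of 0.3, or to 78.1% at 0.5. Splitting the analyses fully by subtype is not a reasonable alternative: with about 10 patients per cell, the plan's own two-sample calculation gives 56% power.

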### **Exclusion Criteria (all must be “no”)**

○ Older than 50 years of age at migraine onset	Yes	No
○ History of cluster headache or hemiplegic migraine	Yes	No
○ Continuous headache	Yes	No
○ Opioid or butalbital meds on 6 or more days per month	Yes	No
○ History of major psychiatric disorder	Yes	No
○ History of medical condition that contraindicates research participation	Yes	No
○ No preventive therapeutic response to 4 or more medication classes	Yes	No
○ Concomitant use of 3 or more meds for migraine prevention	Yes	No
○ Botulinum toxin in head or neck within 4 months	Yes	No
○ Ergotamines, steroids, or triptans for migraine prevention within 2 months	Yes	No
○ Procedures for migraine prevention within 2 months	Yes	No

○ Investigational meds or devices within 90 days	Yes	No
○ History of MI, stroke, TIA, unstable angina, CABG or other revascularization Procedure within 12 months	Yes	No
○ Contraindications to MRI	Yes	No

#### Exclusion Criteria (cont.)

○ Factors that reduce MR image quality	Yes	No
○ Sensory disorders that affect sensory testing	Yes	No
○ Pregnancy	Yes	No
○ Lactation	Yes	No
○ Not using reliable contraception (if woman of childbearing potential)	Yes	No
○ Currently receiving treatment in another study	Yes	No
○ Has received CGRP monoclonal antibody within prior 4 months	Yes	No
○ Active chronic pain condition	Yes	No
○ Acute pain condition	Yes	No
○ Unable to provide informed consent	Yes	No
○ Less than 80% compliant with headache diary	Yes	No

### **Demographics**

DOB: \_\_\_\_ / \_\_\_\_ / \_\_\_\_  
Month Day Year

Current age (years): \_\_\_\_\_

Gender (circle one):      1 = Man      2 = Woman      3 = Other

Sex at Birth (circle one):      1 = Male      2 = Female

Race (circle all that apply):

1 = American Indian/Alaska Native      2 = Asian

3 = Black/African American      4 = Native Hawaiian/Other Pacific Islander

5 = White/Caucasian      6 = Other \_\_\_\_\_

Ethnicity: 1 = Hispanic      2 = Non-Hispanic

Handedness: 1 = Right Handed      2 = Left Handed

### **Vital Signs**

Heart Rate:        \_\_\_\_ beats per minute

Blood Pressure:    \_\_\_\_ / \_\_\_\_ mmHg

Respiratory Rate:    \_\_\_\_ breaths per minute

Temperature (oral):    \_\_\_\_ °F

### **Urine Pregnancy Test**

Result (circle one):      Positive      Negative      N/A

